#### **Statistics**

#### Power and sample size

To gain a general appreciation for the required sample size to detect an indirect effect through the primary mediators (Caregiver Distress, Wellbeing, and Harsh Parenting), we used the sample size estimator for joint significance indirect effects developed by Vittinghoff and Neilands (2015). With a two-sided alpha of 0.05, for an intervention-mediator error term correlation coefficient of 0.2, a standard deviation of the mediator of 0.2, and a standard deviation of the random error term of 0.5, a sample of 425 caregivers per group would be sufficient to detect a mean difference of 0.4 (Vittinghoff & Neilands, 2015). All parameter estimates are based on our previous work. Sample size estimators for multiple mediator models are currently unavailable (VanderWeele, 2016); however, O'Rourke and Mackinnon (2015) provide evidence that multiple mediator models have more power than single mediator models. Thus, we expect this study to have sufficient power for multiple mediator models. With a 10% attrition we expect to have 468 families per group with 234 children, totaling 936 caregivers and 468 children. With a total of 40 intervention groups, the final sample size is 960 caregivers (equivalent of 480 families or more) and 400 index children.

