#### **Analyses**

The statistical analyses will be carried out by the trial statistician, who will remain masked to the group randomization until the main analyses are complete. The analyses outlined in this strategy will be primarily based on an intention to treat; a per protocol analysis will be the secondary analysis. The per protocol analysis will include participants who complete the intervention, with completion defined as attending at least seven of the nine sessions, and will exclude any participant who attended fewer than seven sessions. We have powered the study (see the "Sample size" section) as a superiority study at 10 weeks. The first stage of analyses will be a descriptive model of the data to assess completeness of data and the integrity of the data collection system. Participants and area characteristics and demographics will be summarized at baseline. Clinical characteristics that have been measured repeatedly will be summarized at baseline and at the post-randomization follow-up assessments. In addition, patterns of missing data will be described.

The primary outcomes (total score of parenting scale and proxy-reported child psychosocial wellbeing) will be analyzed using linear mixed models to model the mean difference in the total score of parenting scale 10 weeks post-randomization. The linear mixed models will be adjusted for baseline total scores and stratification. A two-level hierarchical model will be employed to improve power and take into account clustering of the parents at the family level. These models utilize maximum likelihood estimation and thus allow for missing outcome data under the missing at random assumption. Associations between post-randomization variables and missingness will be dealt with by multiple imputation, again

under the missing at random assumption. Departures from this assumption will be assessed with a sensitivity analysis. Secondary outcomes, including parental warmth and responsiveness, harsh parenting, caregiver psychosocial wellbeing, stress, and distress, and self-reported child psychosocial wellbeing will be assessed with a similar methodology used for the primary outcomes, using generalized linear mixed models depending on the type of outcome (normal, ordinal).

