We will investigate the mediation process of different aspects of caregiver wellbeing and parenting and, through that, examine how these factors affect child wellbeing, helping us understand how best to achieve downstream effects on child wellbeing through psychological interventions. Some of the pathways of interest are illustrated in Figure 4.

[figure not shown]

[figure not shown]
Figure 6 Primary mediation pathways

If the efficacy analysis shows significant between-group differences in the mediators (caregiver stress, caregiver distress, caregiver psychosocial wellbeing, and parenting), then we will use parametric regression models to:

[figure not shown]
- Test for mediation of the intervention on child wellbeing through caregiver stress
- Test for mediation of the intervention on child wellbeing through caregiver distress
- Test for mediation of the intervention on child wellbeing through caregiver psychosocial wellbeing
- Test for mediation of the intervention on child wellbeing through parenting

Since all the measures are continuous, the indirect effects will be calculated by multiplying relevant pathways and bootstrapping will be used to produce valid standard errors for the indirect effects. All analyses will adjust for baseline measures of the mediators (caregiver stress, caregiver distress, caregiver psychosocial wellbeing, and parenting), the outcome (child wellbeing) and putative measured confounders (e.g., socioeconomic status).

Furthermore, these factors will also be analyzed through three sequential mediation models (Figure 5), to assess how the downstream effect of BeThere on child wellbeing is mediated first through (1) caregiver wellbeing, (2) caregiver distress, and (3) caregiver stress, and then through parenting.

Finally, we will also measure the effect of BeThere on caregiver wellbeing, stress, and distress, as mediated through cohesion among the intervention group (Figure 6).

We will assess for the effect of the BeThere intervention on each one of the multiple continuous mediators with the use of linear regression models. We chose an a priori *p*-value of lower than 0.15 to select the appropriate mediators to include in our final mediation analysis (VanderWeele & Vansteelandt, 2014). Multiple mediators require independence with each other. Therefore, we will test independence by examining partial correlations between our mediators after accounting for treatment allocation.

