#### Full structural model

For the post-intervention showing a significant intervention effect on children's psychosocial wellbeing, a parametric structural equation modelling approach, which is a statistical technique to test different pathways of the intervention effect on children's psychosocial

wellbeing (Structural Equation Modeling package in Stata version 18.0) will be used. We will estimate the total effect: the natural indirect effects (NIE), and natural direct effects (NDE) of BeThere on child psychosocial wellbeing for; (i) caregiver's scores (primary) and (ii) caregiver's scores (secondary) on Caregiver Distress, Caregiver Psychosocial Wellbeing and Harsh Parenting. The NDE represented the effect of BeThere on Child Psychosocial Wellbeing-parent report that was independent of Caregiver Psychological Distress, Caregiver Psychosocial Wellbeing, Caregiver Harsh Parenting. Caregiver Stress and Caregiver Stress Management. An NIE represented the proportion of BeThere that could be explained by its effect with changes in Caregiver Psychological Distress, Caregiver Psychosocial Wellbeing, Caregiver Harsh Parenting. Caregiver stress and Caregiver Stress management. To quantify the magnitude of mediation, the study will estimate the proportion of the effect mediated by Caregiver Psychological Distress, Caregiver Psychosocial Wellbeing, Caregiver Harsh Parenting., Caregiver stress and Caregiver Stress management (NIE/[NDE + NIE]). All analyses will be estimated using bootstrapping (500 replications) to recover the correct SEs for direct and indirect effects Results are presented as coefficients and 95 % confidence intervals from linear regression. Statistical significance was set a priori at p < 0.05 with no adjustment for multiplicity. Primary mediation analyses will be conducted using data from female caregivers, and secondary mediation analysis using combined data from male and female caregivers for each one of the multiple mediators.

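### The secondary mediation analysis that pools male and female caregivers makes no allowance for family clustering, although the efficacy model does

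*Protocol*

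**What the plan says.** **Design.** Protocol, Randomization, allocates by family so that caregivers of one family share an arm. Protocol, Participants, enrols both caregivers of a two-caregiver family and single caregivers otherwise: 960 caregivers from at least 480 families. There is one index child per family, and each caregiver answers the parenting and child wellbeing questions about that child.

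**Efficacy model.** Protocol, Analyses, uses a two-level linear mixed model to "take into account clustering of the parents at the family level". Secondary outcomes, including caregiver stress, distress and wellbeing, get a similar approach.

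**Mediation.** The same section then assesses the intervention effect on "each one of the multiple continuous mediators with the use of linear regression models", keeping mediators with p below 0.15. Under Full structural model it specifies structural equation modelling in Stata and says: "All analyses will be estimated using bootstrapping (500 replications) to recover the correct SEs for direct and indirect effects". Results are to be reported with 95% intervals from linear regression. "Statistical significance was set a priori at p < 0.05 with no adjustment for multiplicity". The primary mediation analysis uses female caregivers only. The secondary one is a "secondary mediation analysis using combined data from male and female caregivers for each one of the multiple mediators".

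Neither mediation description mentions a family random effect, a clustered variance or the unit that the bootstrap resamples.

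**The concern.** In pooled data, two rows from one family share the arm, the household and the rated child. A linear regression treats them as independent, and so does a bootstrap that draws individuals. Neither gives the correct standard errors that the protocol claims for its bootstrap unless the within-family correlation is zero.

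The protocol is also uneven with itself. The arm effect on stress, distress and wellbeing is estimated once with a family level (efficacy) and once by plain linear regression (mediator screen).

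The pooled analysis is labelled secondary, but it carries weight. Mediation is a stated objective, and the sample size was set for it at 425 caregivers per group. If nearly all families have one male and one female caregiver, 480 families give about 480/2 = 240 women per arm before attrition. Only the pooled data then reach the planned number. Intervals that are too narrow would overstate the evidence for the mediation pathways, and no multiplicity adjustment offsets this.

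**Working it through.** **Plan's own figure.** The documents give no within-family ICC and no design effect, so there is nothing to reproduce on this point. The 425 per group comes from a single-mediator formula without a family term and does not decide the question.

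**Inputs**
- From the protocol: allocation by family; at most two caregivers per family on the stated design; 960 caregivers; nominal levels 0.05 (mediation tests) and 0.15 (screen).
- Assumed: residual within-family ICC ρ of 0.1, 0.3 and 0.5; first with every caregiver in a pair, then with half of them.

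**Step 1: arm effects (treatment-to-mediator path).** With arm constant within a family and a share p of caregivers in pairs:
- Design effect D = 1 + pρ.
- Unclustered SE / correct SE = 1/√D.
- True two-sided error at nominal α = 2 × [1 − Φ(z/√D)], with z = 1.960 for α = 0.05 and 1.440 for α = 0.15.
- Effective number of caregivers = 960/D.

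All caregivers in pairs (p = 1):

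| ρ | D | SE ratio | SE too small by | True error, nominal 5% | True error, nominal 15% | Effective n of 960 |
|---|---|---|---|---|---|---|
| 0 | 1.0 | 1.00 | 0% | 5.0% | 15.0% | 960 |
| 0.1 | 1.1 | 0.95 | 5% | 6.2% | 17.0% | 873 |
| 0.3 | 1.3 | 0.88 | 12% | 8.6% | 20.7% | 738 |
| 0.5 | 1.5 | 0.82 | 18% | 11.0% | 24.0% | 640 |

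Example, ρ = 0.3: 1/√1.3 = 0.877; 1.960 × 0.877 = 1.719; 2 × [1 − Φ(1.719)] = 0.086.

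Half of caregivers in pairs (p = 0.5), ρ = 0.3: D = 1.15, SE ratio 0.93, true error at nominal 5% of 6.8%.

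**Step 2: indirect effect.** The indirect effect multiplies two paths, and the mediator-to-outcome path is less affected by pairing, so this was simulated: 480 two-caregiver families, arm assigned by family, 200 trials per scenario, 500 bootstrap draws. The path effects were assumed (treatment to mediator 0.3, mediator to outcome 0.2, direct 0.1).

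| Mediator ICC / outcome ICC | Individual-resampled SE ÷ family-resampled SE, indirect effect |
|---|---|
| 0 / 0 | 1.00 |
| 0.1 / 0.3 | 0.97 |
| 0.3 / 0.3 | 0.91 |
| 0.5 / 0.5 | 0.84 |
| 0.5 / 0.7 | 0.83 |

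So the indirect-effect SE is about 3% to 17% too small with positive ICCs. The ratios carry a small simulation error.

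**Step 3: female-only analysis.** With one woman per two-caregiver family there are no pairs, so D = 1 and the standard errors do not change.

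**The case against.** The strongest reply is that the protocol never says the bootstrap draws individuals. The resampling unit and variance estimator are often left to a statistical analysis plan, and the efficacy section shows that the authors know about family clustering. It is true that the unit is unstated. A reader might infer that the protocol specifies an unclustered bootstrap, and the text does not support that. The point survives because the protocol names a method (linear regression, with intervals from it), claims that the standard errors will be correct, and departs from its own efficacy model on the same variables. That is more than silence.

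A reader might also infer that all the mediation models are affected. They are not: the primary analysis is female-only. Nor are the models only ordinary regressions, since a structural equation approach is named as well.

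The gates also count. The mediator-specific models run only after significant efficacy results on the mediators, which on the natural reading come from family-level models. The structural model runs only after a significant effect on child wellbeing. If that gate precedes the screen, a null mediator must first pass a clustered test, and the inflated screen rates matter much less. The protocol does not say which caregivers enter the screen or how gate and screen are ordered. Gates do not widen an interval once a pooled model is fitted.

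Finally, the ICC is assumed, what matters is the residual ICC after baseline adjustment, and single-caregiver families dilute the effect. All of this stands, and it is why the range starts low.

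**Conclusion.** The concern holds for the secondary pooled mediation analysis, and for the p<0.15 screen if that uses pooled caregivers. Followed literally, the text gives standard errors that are too small whenever the residual within-family correlation is positive. That is plausible for two adults in one household rating one child, and the protocol's own family level allows for it.

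The size is modest to moderate. Arm-effect standard errors are about 5% to 18% too small, and the true error is about 6% to 11% at nominal 5%, for a residual ICC of 0.1 to 0.5 with two caregivers in every family. Indirect-effect standard errors are about 3% to 17% too small if individuals are resampled, under the simulated mediator ICCs of 0.1 to 0.5 and outcome ICCs of 0.3 to 0.7. Both shrink with single-caregiver families and vanish at ICC 0.

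It would go too far to fault the 500 replications or the interval type. About 3% simulation error in a standard error (1/√(2 × 499) = 0.032) is tolerable and does not favour narrow intervals, and the protocol does not fix how the intervals for indirect effects are formed.

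**What to change.** In Protocol, Analyses and Full structural model, state that:
- every mediation model and every mediator screen fitted to pooled male and female caregivers uses a family random intercept or family-clustered standard errors, in line with the efficacy model;
- the bootstrap resamples whole families, that is, both caregivers together with their index child;
- the p<0.15 screen is run on a named set of caregivers (female only or pooled).

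More bootstrap draws and percentile intervals are optional.

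The cost is a few sentences and some computing time, with no change to data collection. The downside is somewhat wider intervals in the pooled analysis.

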## Oversight, ethics and dissemination

### **Trial oversight**

First, a Trial Management Committee will consist of the Principal Investigator, the Co-Investigators, the Scientific Coordinator, and the in-country Research Coordinator. This committee will monitor the progress of the trial. Trial monitoring will also comprise the collation and reporting of routine trial process indicators and (serious) adverse events ([S]AEs). The research coordinator will receive weekly supervision from the scientific coordinator and senior research staff, and the BeThere trainer and supervisors will receive their own supervision weekly from War Child's psychosocial advisors. The PI will hold weekly meetings with the scientific coordinator and research coordinator to review all activities and issues and ensure fidelity to the research protocol.

Second, a Data Safety Management Committee (DSMC) will be set up to review the SAEs and subsequent actions taken and monitor whether the trial poses a risk to the participants. Summary statistics and graphs showing trends over time will be compiled for the process indicators. No interim analyses are planned.

#### Adverse events

As standard procedure throughout the research, the occurrence of specific adverse events will be monitored and acted upon using the War Child's Adverse Events (AE) Reporting Mechanism. The DSMC will provide oversight on AEs and safety protocols for the study. The DSMC will be composed of individuals to be named prior to the start of the trial, none of whom will be a part of this study. The key terms of reference for the DSMC will be to review reports of AEs (within 48 hours of notification). The purpose of the DSMC is to monitor the occurrence of AEs and where required make decisions on further actions to be taken to determine whether AEs are likely to be related or unrelated to the intervention. The DSMC

will have the mandate to recommend stopping the study if it is determined that the risks of the study outweigh the benefits. All AEs reported spontaneously by participants or observed by the investigators or other staff members will be recorded by the research team on WCH's Adverse Event reporting form. AEs can be detected by anyone as all study staff will be trained in their detection and management. Intervention facilitators will initially discuss AEs reporting with their supervisor, who will report this to the research coordinator and scientific coordinator. Research assistants will initially discuss AE reporting with the research coordinator and scientific coordinator. The scientific coordinator will subsequently share all AEs with the PI, who will be responsible for ensuring appropriate responses to all AEs. All AEs will be reported to the DSMC. This will occur within 24 hours for AEs. The chair or nominated person from the DSMC will review AEs within 48 hours and the DSMC will review all AEs monthly and where necessary to determine whether AEs are likely to be related or unrelated to the intervention.

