#### **Exclusion** criteria

- Under 18 years of age
- Participation by either caregiver in a parenting or stress management intervention in the past six months
- Family does not have a child aged 3–14 years

- Anyone who is unable, even with assistance, to complete the assessment questionnaires
- Unwillingness of either caregiver to give informed consent
- Not fluent in Dinka

Based on the successful implementation of the design in the pilot RCT and RCT in Lebanon, a waitlist control will serve as the comparison group in this study. Participants in the waitlist control group will be given the opportunity to participate in the intervention after the 3-month follow-up assessment has been completed.

This study will involve a waitlist control group for two key reasons:

- 1) While the risk of a nocebo effect among research participants randomized into the control group in waitlist-controlled psychological treatment trials has been raised (Furukawa et al., 2014; Gold et al., 2017; Steinert et al., 2017), there is currently little evidence to show that this is the case for preventative interventions (Gold et al., 2017; Miller, et al., 2023).
- 2) The BeThere intervention has already been shown to be effective among caregivers in Lebanon. Considering the vulnerability of the target population and the lack of existing mental health and psychosocial support services, we do not want to deny control group participants access to the intervention.

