**Table 5: SPIRIT Flow Chart** 

Tuble 3. SPIRIT Flow C	STUDY PERIOD								
	Enrolment	Enrolment Baseline Midline Endline 3-month Follow-							
TIMEPOINT	-t 1	то	t 1	t 2	t 3				
ENROLMENT:									
Eligibility screen	Х								
Informed consent	Х								
Allocation		х							
INTERVENTIONS:									
BeThere		+							
Waitlist-control		+							
ASSESSMENTS:									
Caregivers :									
Demographics		Х		Х	X				
Parenting		Х		Х	Х				
Caregiver wellbeing		Х	Х	Х	Х				
Caregiver stress		Х	Х	Х	Х				

Caregiver distress	Х	Х	Х	Х
Child wellbeing	Х		Х	Х
Group cohesion	Х	Х	Х	Х
Mechanisms of Action	х	Х	Х	Х
Contamination			Х	
Child :				
Child wellbeing	х		Х	Х
Parenting	Х		Х	Х

All questionnaire data will be gathered using tablets, using the software program Kobo, which allows questionnaires to be completed and uploaded without paper and pencil. Kobo is available free of charge from the Harvard Humanitarian Initiative (https://www.kobotoolbox.org/). Measures will be administered in Dinka to each caregiver and child individually by trained and supervised research assistants.

The 15 research assistants will work together under the direction of the research coordinator during data collection periods. Data collection and the start of the intervention groups will take place in a staggered approach over a five-week period with one location starting each week, outlined in Table 2. We estimate that the total sample size when including index children aged 7–14 will be 1,360 (960 caregivers and 400 children), with an average sample of 272 participants per location.

est. # of partici pants	Week1	Week2	Week3	Week4	Week5	Wk 6	Wk 7	Wk 8	Wk 9	Wk 10	Wk 11	Wk 12	Wk 13		Wk 15
272	Baseline, consent, randomi- zation	Session1	Sesssion2	Session3	Session4	Nidline	\$6	S7	\$8	S9	End line				
272		Baseline, consent, randomi- zation	Session1	Sesssion2	Session3	S4	%55 Midline	\$6	S7	\$8	S9	End line			
272			Baseline, consent, randomi- zation	Session1	Sesssion2	S3	S4	S5 Midline	\$6	\$7	S8	S9	End line		
272				Baseline, consent, randomi- zation	Session1	S2	S3	S4	Midline 55	\$6	S7	S8	S9	End line	
272					Baseline, consent, randomi- zation	S 1	S2	53	54	Midline 55	S6	S7	S8	S9	End line

**Table 6** Baseline, midline, and endline data collection schedule

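### Adverse events are recorded only when volunteered or noticed, and BeThere caregivers meet staff about 12 times against 3 on the waitlist, so recorded events cannot be compared between arms

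*Protocol*

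**What the plan says.** The Adverse events section states how events enter the record: "All AEs reported spontaneously by participants or observed by the investigators or other staff members will be recorded". Detection is open to all staff: "AEs can be detected by anyone as all study staff will be trained in their detection and management". The section opens by saying that "the occurrence of specific adverse events will be monitored and acted upon" through an in-house mechanism, but it does not list those events or say whether participants are asked about them.

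Two reporting routes are given. One runs through the groups: "Intervention facilitators will initially discuss AEs reporting with their supervisor". The other runs through the assessments: "Research assistants will initially discuss AE reporting with the research coordinator and scientific coordinator". Only BeThere caregivers have facilitators during the comparison period, because the waitlist is offered the intervention after the 3-month follow-up.

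Table 5 has rows for demographics, the outcome scales, group cohesion, mechanisms of action and contamination. It has none for adverse events.

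The Data Safety Management Committee (DSMC) reviews events, judges whether they are related to the intervention, and may recommend stopping if risks outweigh benefits. Under Trial oversight the protocol adds: "No interim analyses are planned".

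**The concern.** When events are captured passively, the number recorded depends on how often someone is present to hear or see them. Here that differs between arms by design. BeThere caregivers meet trained staff weekly, and those staff have weekly supervision at which to pass events on. Waitlist caregivers meet staff only at the assessments.

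With the same true event rate in both arms, BeThere would be expected to show more recorded events. That could look like a harm of the intervention, or it could leave events on the waitlist unseen. The second possibility matters because the waitlist rationale itself mentions "the risk of a nocebo effect among research participants randomized into the control group". At stake is whether the adverse-event information can support a judgement of relatedness, a weighing of risk against benefit, or a final safety statement that sets one arm against the other. No later analysis can recover events that nobody asked about.

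**Working it through.** The protocol gives no event rate, event count or contact ratio, so there is no stated figure to reproduce.

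**Step 1: scheduled contacts after randomisation.** Inputs: nine weekly sessions (Intervention); four assessments, with randomisation after the first, so three remain (Randomization; Baseline, midline, endline, and follow-up assessments); no sessions for the waitlist before follow-up (Exclusion criteria).

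- BeThere 9 + 3 = 12; waitlist 3; ratio 12/3 = 4.0.
- Counting baseline: 13/4 = 3.25. To endline only: 11/2 = 5.5.
- Midline at the same visit as session 5: 11/3 = 3.67. Seven of nine sessions attended: 10/3 = 3.33.

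About four is a fair summary; these variants run from 3.25 to 5.5.

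**Step 2: all events early, no true difference.** Let p be the chance that one contact captures an event. This is an assumption, since the protocol gives no value. The share recorded is 1 − (1 − p)^k, with k = 12 or 3.

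- p = 0.05: 0.460 vs 0.143, ratio 3.2
- p = 0.10: 0.718 vs 0.271, ratio 2.6
- p = 0.30: 0.986 vs 0.657, ratio 1.5

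**Step 3: events spread evenly to follow-up.** Table 6 puts sessions 1 to 9 in weeks 1 to 9 after the baseline week, midline in week 5 and endline in week 10. Follow-up is assumed to fall 13 weeks after endline, in week 23. Contacts still to come for an event in each of the first ten weeks are:

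- BeThere: 12, 11, 10, 9, 8, 6, 5, 4, 3, 2
- Waitlist: 3 in each of the first five weeks, 2 in each of the next five

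In the last 13 weeks one contact remains in each arm. Summing 1 − (1 − p)^k over the 23 weeks:

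- p = 0.05: BeThere 2.915 + 13 × 0.05 = 3.565; waitlist 1.201 + 0.65 = 1.851; ratio 1.9
- p = 0.10: 4.920 + 1.30 = 6.220; waitlist 5 × 0.271 + 5 × 0.190 + 1.30 = 3.605; ratio 1.7
- p = 0.30: 8.481 + 3.90 = 12.381; waitlist 5.835 + 3.90 = 9.735; ratio 1.3

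**Step 4: private interviews capture more than group sessions.** If an individual assessment is assumed to capture an event with chance 2p and a session with chance p, the even-spread ratios fall to about 1.4, 1.3 and 1.04.

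**Step 5: under the fix.** Solicited contacts are 3 vs 3, a ratio of 1.0.

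**The case against.** The strongest reply is that the protocol plans no comparison of event counts by arm. It describes review of individual cases within a set time and a judgement of relatedness for each; no by-arm table, rate or test of adverse events is planned. A reader might infer that the DSMC decides on skewed counts, but the text does not say so. That part of the reply stands. It does not remove the point, because relatedness and risk against benefit still rest on information gathered unevenly, and so would any report of events by arm.

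Second, a reader might infer that worsening on the waitlist goes unrecorded. The documents do not support that. Table 5 measures caregiver distress, stress and wellbeing in both arms at all four time points. A harm of waiting that showed on those scales would be seen. The gap is in adverse events.

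Third, the in-house mechanism, its form and the data collection instruments in the appendices are not shown. Table 5 is also not exhaustive: the Masking section requires a check on unmasking of research assistants at each time point, and the table has no row for it. So solicited questions may exist outside the text. As written, however, the stated rule is spontaneous report or observation.

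Fourth, a fourfold contact ratio does not mean a fourfold distortion. The larger ratios require every event to fall soon after randomisation and a group session to elicit disclosure as well as a private interview. This stands, and the range above allows for it. The waitlist interviews planned under Qualitative Data Collection add little contact, since key informant interviews number at most 30.

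**Conclusion.** The point holds as a weakness of design, not as an error of fact or a contradiction. Under the rule as written, adverse events are likely to be over-recorded in BeThere relative to the waitlist, and they cannot be read as a comparison of arms.

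The direction rests on one assumption: more contact with staff yields more reports. The size is unknown. For assumed capture chances of 0.05 to 0.30 per contact, the spurious ratio is about 1.3 to 1.9 with events spread evenly to a follow-up 13 weeks after endline, and 1.5 to 3.2 if all occur early. It is smaller still if individual interviews capture more than group sessions. The conclusion also depends on the undescribed in-house mechanism containing no equal, solicited enquiry in both arms. The analysis of parenting and the other scale outcomes is not affected.

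**What to change.** Add an adverse-event row to Table 5: the same short, fixed questions to every caregiver in both arms at midline, endline and 3-month follow-up. Ask them last, and word them without reference to sessions. Keep the existing instruction to stop participants from disclosing their assignment, and the existing check on unmasking at each time point.

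State that any between-arm comparison of adverse events uses these solicited events only. Events found in sessions or reported spontaneously are still acted on as now, and are listed separately by source. If the in-house mechanism already includes such questions, describing them in the protocol would be enough.

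A by-arm count of worsened distress for the DSMC is not needed. It would be a look at a secondary outcome during the trial, which sits awkwardly with the statement on interim analyses.

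The cost is a few minutes per interview at visits already planned, a change to the form, and more unrelated events on record. There is also a small risk that an answer at midline or endline unmasks an assistant for later assessments; asking last protects only the outcomes already collected at that visit.
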